3.3 Study Duration and Dates

Study Inclusion: 9 months

Study duration: 3 years

3.4 Safety and Efficacy Monitoring

Version 1.3; Date: 3/14/2016

We will perform 4 MRIs during the course of the radiation therapy as a part of this research study. Each of these 4 research MRIs possesses no additional risk compared to the standard MRI techniques. Each MRI will be obtained with gadolinium based contrast administration approved for clinical usage. We will use gadoteridol (Prohance, Bracco Diagnostics Inc. NJ)

As described above, risks associated with the research MRIs are no different from the risks associated with a routine clinical MRI. If any adverse event occurs, the patient will be excluded from the study for the subject's best interest. Additionally, the subject may withdraw himself/herself his/her consent at any point of time. All the standard MRI safety precaution will be taken before the image acquisition. As we do not anticipate any adverse event related to the research sequences, no specific precaution related to this study is needed. We will closely monitor the patient during the scanning. Appropriate patient care will be taken should there any adverse event.

This study is aimed to quantify response of standard clinical treatment using advanced MRI technique and has NO therapeutic component. The change seen on the imaging during therapy will not be used for any clinical decision making as we do not know the clinical significance of these changes.

The included subjects will be monitored for potential side effects of contrast injection as per clinical standards. Any side effects, which has been described in <1% of patients, will be managed as per clinical standards.

In addition, gadolinium contrast agents have been associated with nephrogenic systemic fibrosis in patients with severe renal functions. We will not include any subject in this study with chronic severe kidney disease (GFR<30 mL/min/1.73 m²) or acute kidney injury.

3.4.1 Independent Data Monitoring Committee

NA

3.5 Ethical Considerations

This study will be conducted in accordance with Good Clinical Practice, the Declaration of Helsinki, and 21CFRPart50 – Protection of Human Patients, Part 56 –Institutional Review Boards, and the other applicable local ethical and legal requirements.

The Ethics Review Committee/Institutional Review Board (IRB) must be constituted according to Code of Federal Regulations (CFR).

The IRB will be informed by the principal Investigator of all subsequent protocol amendments and of serious or unexpected AEs occurring during the study, which are likely to affect the safety of the patients or the conduct of the study.

3.6 Informed Consent

The principles of informed consent in the current edition of the Declaration of Helsinki will be implemented in this study. A written informed consent will be obtained in accordance with 21CFR50.25 and 21CFR50.27 before the protocol – specified procedures are carried out. Patients, their relatives, guardians or, if necessary, legal representatives must be given ample opportunity to inquire about details of the study.

The consent form generated by the Principal Investigator must be approved (along with the protocol) by the applicable IRB. Consent forms must be in a language fully comprehensible to the prospective patient. The consent form should be signed and dated by the patient or the patient's legally authorized representative, and the investigator. Each patient's signed informed consent form must be kept on file by the investigator for possible inspection by Regulatory Authorities and sponsor (UAB).

3.7 Confidentiality

Patient names will not be supplied in the sponsor data. Only the patient number and patient initials will be recorded in the CRF, and if the patient name appears on any other document (e.g., laboratory report), it must be obliterated on the copy of the document to be supplied by the sponsor. Study findings stored on a computer will be stored in accordance with local data protection laws. The patients will be informed that representative of the sponsor, independent IRB, or regulatory authorities may inspect their medical records to verify the information collected, and that all personal information made available for inspection will be handled in strictest confidence and in accordance with local data protection laws.

The investigator will maintain a personal patient identification list (patient numbers with the corresponding patient names) to enable records to be identified.

4.0 SELECTION OF PATIENTS

4.1 Number of Patients

Approximately 20 patients should be enrolled and treated in this study. It is planned to recruit this sample in 9 months.

4.2 Inclusion Criteria

See above.

4.3 Exclusion Criteria

See above.

4.4 Patients of Reproductive Potential

The patient must not be pregnant or breast-feeding at enrollment in the study. Absence of pregnancy must be demonstrated by serum or urine testing prior to radiation therapy.

Female patients of child bearing potential (i.e., ovulating, premenopausal, not surgical sterile) must use a medically accepted contraceptive regimen. Male patients must agree to use a medically approved method of contraception.

If a female patient becomes pregnant during the study, the subject will be withdrawn from the study.

5.0 STUDY TREATMENTS

This is an observational study attempting quantification of imaging changes related to STANDARD radiation treatment given with temozolomide. No investigational therapy will be given to the study subjects.

6.0 STUDY PROCEDURES AND SCHEDULE**6.1 Screening Phase**

Each potential patient will be examined before the start of the study to determine their eligibility for participation by the investigators. Vital signs and complete blood count will be obtained during radiation treatment as per the clinical standard of care. Female patients of childbearing age will be tested for serum beta-hCG.

6.2 Study Days

The following tests/procedures will be completed prior to each MRI:

(1) Vital signs: The research coordinator will take the vital signs before the MRI.

6.3 Follow-up

The final intervention as a part of this research study is to acquire the 4th MRI, which we plan to obtain at the completion of the current clinical standard of care radiation therapy. No therapy is part of this study. However, all included subjects will be followed-up for 24 months from the time of diagnosis. During the follow-up period each patient will be imaged and evaluated according to clinical standard of care. We will document the followings:

Progression: We will assess time to progression as well as site progression.

Progression will be determined by the RANO¹⁹ criteria as described in the Table 1:

Criteria for Determining First Progression Depending on Time From Initial Chemoradiotherapy

First Progression	Definition
Progressive disease < 12 weeks after completion of chemoradiotherapy	Progression can only be defined using diagnostic imaging if there is new enhancement outside of the radiation field (beyond the high-dose region or 80% isodose line) or if there is unequivocal evidence of viable tumor on histopathologic sampling (eg, solid tumor areas [ie, > 70% tumor cell nuclei in areas], high or progressive increase in MIB-1 proliferation index compared with prior biopsy, or evidence for histologic progression or increased anaplasia in tumor). Note: Given the difficulty of differentiating true progression from pseudoprogression, clinical decline alone, in the absence of radiographic or histologic confirmation of progression, will not be sufficient for definition of progressive disease in the first 12 weeks after completion of concurrent chemoradiotherapy.
Progressive disease ≥ 12 weeks after chemoradiotherapy completion	
 • New contrast-enhancing lesion outside of radiation field on decreasing, stable, or increasing doses of corticosteroids. • Increase by ≥ 25% in the sum of the products of perpendicular diameters between the first postradiotherapy scan, or a subsequent scan with smaller tumor size, and the scan at 12 weeks or later on stable or increasing doses of corticosteroids. • Clinical deterioration not attributable to concurrent medication

	
or comorbid conditions is sufficient to declare progression on current treatment but not for entry onto a clinical trial for recurrence.
 
• For patients receiving antiangiogenic therapy, significant increase in T2/FLAIR nonenhancing lesion may also be considered progressive disease. The increased T2/FLAIR must have occurred with the patient on stable or increasing doses of corticosteroids compared with baseline scan or best response after initiation of therapy and not be a result of comorbid events (eg, effects of radiation therapy, demyelination, ischemic injury, infection, seizures, postoperative changes, or other treatment effects).
--	---

Abbreviation: FLAIR, fluid-attenuated inversion recovery.

Time to progression and the site of recurrence will be documented.

Survival: After the first recurrence, the study will ONLY document the survival time. No other patient parameter will be recorded for this study.

6.4 Enrollment and Randomization Procedures

Eligible patients will be enrolled into the study through the UAB Department of Radiology Research Administration office ([contact]). After the patient is scheduled to have the radiation therapy, the investigators will evaluate for inclusion and exclusion criteria. When a subject meets the inclusion and exclusion criteria, one of the investigators will communicate with the potential subjects describing the study. If a subject is interested, a consent form will be sent the patient using UAB Patient Portal. The research coordinator from the Radiology Research Administration office will consent the subjects.

This study is not a RANDOMIZED study.

7.0 EFFICACY AND SAFETY

No investigational drug will be administered as a part of this trial. We are not measuring any efficacy of any treatment modality either as a part of this research study.

8.0 STATISTICAL METHODS

Version 1.3; Date: 3/14/2016

Based on the number of subjects (n=20), our statistical analysis will be largely descriptive and explanatory. Descriptive summary statistics tabulations will be generated for each time point. Means, standard deviations, median, and interquartile ranges will be generated for continuous variables, and frequency and percentages will be generated for categorical variables. For the primary outcome variable, in order to evaluate the within-subjects changes over time we will assess the pair-wise differences between time points using paired t-test, and may also perform repeated measures analysis of variance (ANOVA) on the continuous outcomes and account for the correlative nature of the repeated measurements with the caution and understanding of the limited sample size.

The Kaplan-Meier approach will be used to produce survival curves as well as the median and corresponding 95% confidence limits for time to first recurrence as well as overall survival. Subjects who have not had an event will be censored at the last known date available.

The location of recurrence will be reviewed and classified to then be presented in terms of frequencies and percentages to determine if there can be any dichotomization scheme created. Based on the potential dichotomization, we may use chi-square tests and logistic regression to examine how other factors may be potentially associated with the site of recurrence.

Distributional assumptions of the statistical analysis will be verified, and if the assumptions are not met, then non-parametric analogs will be considered. Statistical significance will be determined based on the two-sided level of significance at the 0.05 level. All analyses will be performed using statistical analysis software SAS version 9.4.

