8.1 Sample size

There were no formal sample size calculations performed for this study, however based on the anticipated number of subjects (n=20), if we assume the largest changes in volume to be between the first and fourth time points, and consider the paired difference in means with correlation ranging from weak to moderate ($\rho=0.1 - 0.6$) we anticipate having 66-88% power to detect statistically significant differences at the 0.05 two sided level of significance.

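### The paired t-tests in 8.0 use only patients with both scans of a pair; with no rule for missing scans, the estimated change can be biased if loss relates to response, and the power in 8.1 allows for no loss

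*Combined protocol and SAP*

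**What the plan says.** Section 3.1 schedules four scans: at baseline and after 20, 40 and 60 Gy. Section 3.2 makes CNI across these scans the primary endpoint, and section 2.0 makes the time course and size of the MRI changes the primary objective. For within-patient change in the primary outcome, section 8.0 states: "we will assess the pair-wise differences between time points using paired t-test, and may also perform repeated measures analysis of variance (ANOVA"). It names no mixed model or other likelihood method. It describes the work this way: "our statistical analysis will be largely descriptive and explanatory". It also sets a test level: "Statistical significance will be determined based on the two-sided level of significance at the 0.05 level".

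The plan foresees patients leaving. Section 3.4 excludes a patient from the study after any adverse event and adds that "the subject may withdraw himself/herself his/her consent at any point of time". Section 4.4 withdraws a patient who becomes pregnant. The only provision for incomplete data is censoring for recurrence and survival (3.2 and 8.0). Nothing is said about missing or unusable scans, analysis sets, replacement of patients or sensitivity analyses.

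Section 8.1 says that no formal sample size calculation was done, but it gives 66–88% power "based on the anticipated number of subjects (n=20"), with within-patient correlation from 0.1 to 0.6. The variable is volume: "if we assume the largest changes in volume to be between the first and fourth time points". Section 4.1 sets enrolment at the same figure: "Approximately 20 patients should be enrolled and treated in this study".

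**The concern.** Four scans make six pairs, and each paired t-test rests on whichever patients have both scans of that pair. The subsets can differ from pair to pair. A patient without scan 4 adds nothing to the scan 1–4 change, even though scans 1 to 3 say something about where that patient was heading. The optional ANOVA, in its classical form, is stricter still, because one missing scan removes the patient altogether.

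If patients who leave differ in response from those who stay, the estimated change describes those who completed the scans and not the patients enrolled. That change is the study's main product, and section 11.2 intends the findings as preliminary data for a grant application. Separately, because enrolment and the number behind the power are both 20, any lost scan 1–4 pair takes the study below its stated power.

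**Working it through.** **1. The stated power.** Inputs from 8.1: n = 20, two-sided α = 0.05, ρ = 0.1 to 0.6, power 66–88%. The documents give no mean change and no SD. For a paired t-test

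d_z = δ / √(s₁² + s₄² − 2ρs₁s₄),

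and power is the probability that a noncentral t variable with n − 1 degrees of freedom and noncentrality d_z√n exceeds t(0.975; n − 1) in absolute value.

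With equal SDs, 66% at ρ = 0.1 implies δ = 0.75 SD (d_z = 0.75/√1.8 = 0.559). The same δ at ρ = 0.6 gives d_z = 0.75/√0.8 = 0.839 and 94.5% power, not 88%. With an assumed 2:1 ratio of SDs between the two scans, the range does come out (66.0% and 88.4%). So the range cannot be verified, but it is not shown to be wrong. I therefore took each end at face value (d_z = 0.559 for 66%, d_z = 0.739 for 88%) and changed only the number of complete pairs:

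| Complete pairs | Low end | High end |
|---|---|---|
| 20 | 66.0% | 88.0% |
| 18 | 60.9% | 84.0% |
| 16 | 55.3% | 78.9% |

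**2. Possible bias in the complete-pair change.** Every input here except ρ is an assumption: unit SDs, equal correlation ρ between all scans, true scan 1–4 change −0.75 SD, and 10% or 20% missing scan 4. The chance of missing scan 4 rises on a logistic scale as the decline from scan 1 to scan 3 gets smaller.

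Write D₃ and D₄ for the changes from scan 1 to scans 3 and 4. Then cov(D₄, D₃) = 1 − ρ and var(D₃) = 2(1 − ρ), so the regression slope of D₄ on D₃ is 0.5. The bias is

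0.5 × √(2(1 − ρ)) × m,

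where m is the mean standardised D₃ among patients who have scan 4. The root is 1.342 at ρ = 0.1 and 0.894 at ρ = 0.6. I obtained m by numerical integration. Overstatement is |bias| / 0.75.

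| Log-odds of loss per SD of D₃ | Missing | m | ρ = 0.1 | ρ = 0.6 |
|---|---|---|---|---|
| 0 | any | 0 | 0% | 0% |
| 0.5 | 10% | −0.049 | 4.4% | 2.9% |
| 0.5 | 20% | −0.096 | 8.6% | 5.7% |
| 1 | 10% | −0.091 | 8.1% | 5.4% |
| 1 | 20% | −0.173 | 15.5% | 10.3% |
| 2 | 10% | −0.143 | 12.8% | 8.5% |
| 2 | 20% | −0.262 | 23.4% | 15.6% |

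For example, the last row at ρ = 0.1 is 0.5 × 1.342 × 0.262 / 0.75 = 23.4%. If the slope of 2 is instead counted per SD of the outcome, it is 2 × 1.342 = 2.68 per SD of D₃ at ρ = 0.1. Then m = −0.291 at 20% missing, and the overstatement is 26.1%. At ρ = 0.6 the same scaling gives 14.8%. The overall ranges are about 3–16% at ρ = 0.6 and 4–26% at ρ = 0.1.

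**3. Direction, and what a likelihood model recovers.** This is a simulation with ρ = 0.5, 20% losing scan 4 through a noisy threshold, and true change −0.75:

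| Loss depends on | Complete pairs | Likelihood estimate, all scans |
|---|---|---|
| nothing related to CNI | −0.75 | −0.75 |
| small decline by scan 3 | −0.88 | −0.75 |
| high baseline CNI | −0.62 | −0.75 |
| small decline at the unseen scan 4 | −1.00 | −0.92 |

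**The case against.** The strongest reply is that the documents give neither an amount nor a cause of scan loss. The routes out that they name (adverse event, withdrawn consent, pregnancy) are not tied to CNI. Entry requires a Karnofsky score above 60 and excludes situations that would limit compliance. The scans fall within the course of radiotherapy, when patients attend for treatment anyway. This stands. A reader might infer that the plan's estimate is biased, or that it overstates the decline. The documents do not support either: under loss unrelated to CNI there is no bias, and under loss of patients with high baseline CNI the sign reverses.

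The percentages also depend on chosen inputs. The top of each range needs a log-odds slope of 2, an odds ratio near 7 per SD, and doubling the assumed change to −1.5 SD halves every figure. At ρ = 0.6 the illustration uses d_z = 0.839, while the power table uses 0.739, so the two should not be read as one scenario.

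Nor is the mixed model a complete cure. It is close to unbiased only when loss depends on scans that were observed. If loss depends on the unseen scan 4 change, with a log-odds slope of 2 and 10–20% missing, it is still off by about 11–33% over ρ = 0.1 to 0.6.

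Two further readings go too far. A patient missing scan 4 is not lost entirely, since that patient still counts in pairs 1–2, 1–3 and 2–3 and in the summaries at each time point. And the power figure says nothing about CNI, because 8.1 speaks of volume.

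Two replies carry less weight. The descriptive aim lowers the stakes, but a descriptive mean is distorted by selective loss just as a test is, and 8.0 sets a significance level. The mention in 8.0 of accounting for correlated measurements could be read as a mixed model, but the text names only ANOVA, and only as an option.

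**Conclusion.** The point holds as a gap in the plan with a conditional consequence. The main analysis uses complete pairs, patients can leave during radiotherapy, and no method covers the scans then missing. Bias arises only if leaving is related to response, and it can go either way. The ranges of 3–16% (ρ = 0.6) and 4–26% (ρ = 0.1) illustrate one mechanism under assumed inputs and are not predictions for this study. The power loss needs no assumption about why scans are missing: holding the effects implied by 8.1, each lost pair costs about 2–3 points, giving 61–84% with 18 pairs and 55–79% with 16. That figure applies to volume and rests on a stated range that cannot be checked from the documents. In a small, largely descriptive study this is a cheap improvement worth making, not a flaw that undermines the design.

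**What to change.** In 8.0, make the main analysis of each continuous measure a mixed model for repeated measures on every acquired scan. Use REML, scan as a four-level factor, and an unstructured covariance with Kenward–Roger degrees of freedom, falling back to heterogeneous compound symmetry if the model does not converge. Take the between-scan changes from this model. Report the number of usable scans and the reasons for loss at each time point, and keep the complete-pair t-tests as a sensitivity analysis.

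In 8.1, say that 66–88% is for volume with 20 complete pairs, and add 61–84% for 18 and 55–79% for 16.

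The cost is SAP wording; SAS 9.4, already named in 8.0, fits this model. With complete data the point estimates are the same as the paired differences. There are three downsides. The model removes bias only if missingness depends on observed scans, and otherwise only reduces it. The unstructured form estimates 14 parameters (4 means, 10 variances and covariances) from 20 patients, hence the simpler fallback. And the power as restated is slightly less favourable.

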8.1 Sample size

There were no formal sample size calculations performed for this study, however based on the anticipated number of subjects (n=20), if we assume the largest changes in volume to be between the first and fourth time points, and consider the paired difference in means with correlation ranging from weak to moderate ($\rho=0.1 - 0.6$) we anticipate having 66-88% power to detect statistically significant differences at the 0.05 two sided level of significance.

9.0 PROTOCOL AMENDMENTS AND LEGAL ASPECTS

9.1. Protocol Amendments

Once the study has started, amendments should be made only in exceptional cases. The changes then become part of the clinical study protocol.

9.2 Approval of the Clinical Study Protocol and Amendments

Before the start of the study, the clinical study protocol, informed consent document, and any other appropriate documents will be submitted to the IRB with a cover letter for a form listing the documents submitted, their dates of issue, and the site (or region or area of jurisdiction, as applicable) for which approval is sought. If applicable, the documents will also be submitted to the authorities, in accordance with local legal requirements.

9.3 Closure of the study

The study must be closed at the site on completion. Furthermore, the sponsor or the investigator has the right to close this study site at any time. As far as possible, premature closure should occur after mutual consultation. Depending on local legislation, it may be necessary to inform IRB and the regulatory authorities when the study site is closed.

Study materials must be returned, disposed of or retained as directed by the sponsor.

9.4 Record Retention

The investigator must obtain approval in writing from the sponsor before destruction of any records.

Essential documents should be retained until at least 5 years after the closure of the study.

Essential documents include:

- Signed informed consent documents for all patients.
- Patient identification code list and enrollment log.
- Record of all communications between the investigator and the IRB.
- Record of all communication between the investigator and the Principal Investigator or Designee.
- List of subinvestigators and other appropriately qualified person to whom the investigator has delegated significant trial-related duties, together with their roles in the study and their signatures.

- Copies of CRFs and of documentation of corrections for all patients.
- All other source documents (patient medical records, laboratory records, etc.).

